Lack of physical activity has been labelled a global pandemic and reported as the 4th leading global cause of death [14]. Physical inactivity increases risk of lifestyle diseases, such as heart disease, type 2 diabetes and cancer, resulting in over 5 million annual global deaths [15]. Further, the estimated annual financial burden of physical inactivity is nearly 54 billion USD in health care costs around the world [16]. There seems to be a drop in physical activity in adolescence and a large part of adolescents are under the recommended physical activity levels provided by the World Health Organization (WHO) [17-19]. Lack of sufficient physical activity tends to continue into adulthood and research suggests that the majority of adolescents in the EU do not even reach 30% of recommended daily physical activity [19-21]. Further, adolescents seem to have the unhealthiest diet of all age groups and adolescence is a particular susceptibility period to weight gain [22]. Research has repeatedly revealed a significant relationship between nutritional behavior and physical activity in terms of weight management [23]. A tremendous increase in global adolescent obesity has been witnessed in the past decades and prevalence for instance tripled since 1975 [24]. Cost-effective interventions to increase physical activity and improve nutritional behavior in adolescent populations are therefore direly needed.

Physical inactivity and inadequate nutritional habits are often interrelated to disabling emotional problems and integrated strategies should include all three pillars to improve physical as well as mental well-being in adolescent populations. Mobile health interventions targeting disabling emotional problems in adolescent populations have revealed encouraging outcome, despite the fact that attrition rates in these interventions are generally high [11, 25-30]. Varying definitions of attrition have complicated research on this topic but attrition is defined as leaving treatment before obtaining a required level of improvement or completing intervention goals [31-33]. Research on mental mHealth interventions among adolescents have frequently lacked detailed time related attrition data alongside accurate definitions and analysis of attrition reasons though recent studies show promise in that regard [11, 30, 34]. Attrition is regularly reported at two distinct points of time; intervention start and at end of intervention. A continuous measure of usage vs. non-usage in mHealth interventions for adolescents while simultaneously obtaining detailed usage data in order to prevent or delay exact times of attrition in future interventions would perhaps be an improved representation of attrition [35].

Increased knowledge on actual attrition factors and patterns in adolescent populations from mHealth interventions are direly needed. Obtaining a better understanding of how motivational support motivates adolescents to use mHealth applications and why they maintain or lose interest in using them to improve their health is of vital importance. Motivational support in mHealth interventions, defined as strategies to enhance motivation and counter attrition to overcome behavior change barriers, often include goal-setting, feedback, social support and rewards (36-37). Systematic reviews examining possible drivers behind usage point to group and task customization, localization, functional user support, gamification of health tasks and immediate visual but simplified feedback on user action while while gender-related motivational support features could be contributing factors [36-38]. Timing of tailored motivational support, through just-in-time adaptive interventions (JITAI), should be considered as well when implementing adolescent mHealth interventions since time-based individualization could counter high attritions rates [35, 39]. Given the magnitude of reported health problems among adolescents and lack of cost-effective health behaviour interventions specifically developed for adolescent populations, the need for better understanding of attrition reasons in adolescent mHealth interventions is massive. The purpose of this study was firstly to seek richer understanding of continuous attrition rates from a mHealth intervention in an adolescent population and what effects motivational support has on attrition rates. Secondly, the aim was to examine effectiveness of the intervention with the aim to increase daily mental, nutritional and physical health behaviour.

Methods

Participants

Participants are adolescents, age 13 to 16 years old, attending one of three public schools for children and adolescents in the greater capital area of Iceland. All children attending the oldest 3 classes, called 8th to 10th classes, in three participating public elementary schools in

Iceland are eligible participants (n=661, m:f ratio=313:348). All children in public schools in the municipality are equipped with an iPad from 10 years of age. Exclusion criteria are diagnosis of severe disorder of intellectual development and/or physical-, developmental- and mental illness significantly restricting ability to use mobile apps. Research specifications and introduction to the application will be sent via email to parents and legal caretakers of all eligible participants through school officials along with confirmative survey link. If the link is answered, it yields confirmation for informed consent. Adolescents with informed consent from parents/legal caretakers will then invited to take part in the study through confirmative survey link. The study has been approved by the National Bioethics Committee (license number: VSNb2015060065/03-01).

Measurements

Original primary outcome measure will be app acceptability and functionality, measured with *Systematic Usability Scale* (SUS), a widely used and relatively well studied 10-item questionnaire on app usability where scores range from 0-100 and total score over 70 yielding satisfactory usability and user acceptance [40, 41]. Further primary measures were amount, frequency and time of daily physical activity measured through in-app activity, self-reported stress levels, quality of sleep and energy levels, measured through levels of the health app usage and completion of in-app health tasks.

Secondary outcome measures include standardized body mass index (*BMI-SDS*) based on BMI index reference values for Swedish children and adjusted for age and sex. Participants are weighed in kilograms in light clothing without shoes using a digital scale (Marel type C2; Marel, Reykjavik, Iceland). Height is measured in centimetres using a wall-mounted stadiometer (Seca stadiometer; Seca, Hamburg, Germany).

Anxiety and depressive symptoms will be assessed using the *Revised Children's Anxiety and Depression Scale* (RCADS), a self-report assessment tool for children and youth. The scale is a four point Likert scale, spans 47 questions and is divided into 6 subscales; separation anxiety symptoms, general anxiety symptoms, obsessive-compulsion symptoms, social anxiety symptoms, panic symptoms, depression symptoms. A *T*-score over 65 marks a clinical cut-off point. The inventory's psychometrics have been studied with acceptable findings in both US and Icelandic paediatric populations [42, 43].

General Self Efficacy Scale (GSE), a 10 item self-report questionnaire with ranging total scores from 10 to 40, is used to measure self-efficacy levels where higher score yielding increases self-efficacy [44]. Acceptable psychometric properties for the questionnaire have been obtained and it is used globally in youth populations [45].

[figure not shown]
BEARS sleep screening algorithm will be used to evaluate participant's sleep problems. It is a sleep screening instrument for children from 2 to 18 years old, divided into 5 sleep domains; bedtime problems, excessive daytime sleepiness, awakenings during night, regularity and

duration of sleep and snoring [46]. The algorithm's psychometrics have been studied with acceptable findings in paediatric populations [47].

mHealth application

SidekickHealth was initially developed through multiple focus group studies amongst both Icelandic elementary school students and adolescents in the obesity clinic at the Landspítali University Hospital in Iceland to incorporate the target groups' needs and opinions. Based on results from focus-group studies and design advisors, the app took the form of a social health game (see Figure 1). Functionality of the app evolves around motivational support to help the user set goals and complete health tasks (gamification of tasks), in three main categories: food and drink (e.g. vegetable and water intake, consumption of fruits, avoiding sugary soda or energy drinks), physical activity (e.g. body-weight exercises, logged minutes of sports activity, gps-based biking, walking or running), and mental health exercises (e.g. reducing stress, exercising gratitude and improving sleep habits). By completing health tasks that are labelled missions and participating in friendly competitions with peers, users earn points (called "kicks") and badges providing altruistic rewards (e.g. litres of water for children in need or polio vaccinations that are sent in their name to children in need through UNICEF). A visual representation of the user's performance is provided in different categories. Keeping the app fun, entertaining, and easy-to-use is of integral importance and was a strong focus point throughout all developmental phases. The smartphone application operates on Android and iOS platforms. The app's function focuses on education and simple health behaviour changes through the benefits of increased physical activity and mental health exercises as well as a healthy diet, portion sizes, and appetite awareness training (AAT). AAT is a behaviour modification tool that has for instance been used in obesity treatment and encourages overweight/obese children and youth to consume food and drink in response to internal appetite cues. It has shown promise for the treatment of overweight and obese children and teenagers and has been visually developed as an individual mission in the app's nutrition category [48, 49]. Participants in the intervention realm will be randomly assigned to groups consisting of 8 individuals which collectively and individually competed in point collection through completion of in-app health tasks. In the beginning of each of the trial's 6 weeks, the intervention group receives in-app messages where a new weekly competition (both individual and on group level) with altruistic rewards is introduced. In weeks 2 to 6, altruistic rewards for past week's efforts will also be handed out. Winners of competitions receive confirmation that UNICEF had sent Polio vaccinations to children in need. Further, through completion of in-app health exercises participants collect litres of water that will be sent in their name to children in need through UNICEF. The total cost for the altruistic rewards for all in-app rewards throughout the treatment period was roughly estimated to be between 50 to 100 US dollars or roughly 50 US cents per participant.

Figure 1. Overview of app functions & categories

[figure not shown]

Procedure

The study is a randomized controlled study. Cluster randomization is used to distinguish three participating schools into control, treatment-as-usual (TAU) and intervention groups. Measures will be obtained at baseline and 42 days later. Participants in both the TAU group and the intervention group receive an approximately 10 minutes long introduction regarding the study specifications and the application. The control group receives no further contact, access to the application or information until study-end questionnaire measures. Participants in the intervention group are randomly assigned to teams consisting of 8 individuals that collectively and individually compete in point collection through completion of in-app health tasks. Participation in the TAU group and intervention group is defined as downloading the Sidekick app and completing at least 3 health exercises within it. Time of exercise is defined as the timestamp on completion of exercise within any of the three types of exercise categories (physical activity, nutrition and mental health) of the app. Exercise frequency refers to how often a given exercise was completed by a participant. Time of attrition was defined as the time stamp of last completing health exercise within the Sidekick throughout intervention period. The procedural difference between TAU group and intervention group evolves around motivational support. The intervention group receives weekly motivational support in form of individual and group feedback on usage, participation in friendly health task competitions and weekly altruistic rewards for usage. Participants in TAU group use the

application individually throughout trial period without any motivational support. A flow chart of participation is displayed in figure 2.

Figure 2. Participant flow chart

Statistical analysis

Descriptive characteristics of participants along with attrition reason are reported. Pearson's correlation coefficient, independent samples *t*-tests, repeated measures ANOVAs with adjusted alpha levels, and χ^2 tests will be used to measure mean differences from baseline to trial's end within and between research groups on primary and secondary outcome measures. Kaplan-Meier survival analysis plots and logrank tests are deployed to assess time of attrition and possible significant differences between and within research groups [50, 51]. Trial beginning is defined as time of first in-app health exercise completion and the trial period was six weeks, or 42 days, from that moment. Attrition, or the event, is defined as the time of participants' last completed health exercise in SidekickHealth. Participants' cases will be evaluated as censored when the application was still being used 42 days after study start. Cox proportional hazard regression models with interacting covariables using research groups as clusters was used to examine attrition prediction based on usage of in-app health exercises between time, type and frequency of exercises as well as sociodemographic variables (age,

gender) [52]. Significance will be defined at $p < .05$. Data was analysed using IBM SPSS Statistics, Release Version 29 (SPSS, Inc., 2009, Chicago, IL, USA, <http://www.spss.com>).

References

1. Smith, A. (2015, April 1). *U.S. Smartphone Use in 2015*. Pew Research Center. <https://www.pewresearch.org/internet/2015/04/01/us-smartphone-use-in-2015/>
2. Silver, L. (2019, February 5). *Smartphone Ownership Is Growing Rapidly Around the World, but Not Always Equally*. Pew Research Center <https://www.pewresearch.org/global/2019/02/05/smartphone-ownership-is-growing-rapidly-around-the-world-but-not-always-equally/>
3. Anderson, M. & Jiang, J. (2018, May 31). *Teens, Social Media and Technology 2018*. Pew Research Center. <https://www.pewresearch.org/internet/2018/05/31/teens-social-media-technology-2018/>
4. Jones, E. A. K., Mitra, A. K. & Bhuiyan, A. R. (2021). Impact of COVID-19 on Mental Health in Adolescents: A Systematic Review. *The International Journal of Environmental Research and Public*, 18(5). <https://doi.org/10.3390/ijerph18052470>
5. Körmendi, A. (2016). Smartphone usage among adolescents. *Psychiatria Hungarica: A Magyar Pszichiátriai Társaság Tudományos Folyóirata*, 30(3), 297-302.

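### SUS, the first-named primary outcome, falls under a change-from-baseline, between-group analysis that does not fit it, and its cut-off of 70 has no planned estimate or population

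*Combined protocol and SAP*

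**What the plan says.** Four parts of the combined protocol and SAP bear on this.

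- **Measurements** opens the list of outcomes with "Original primary outcome measure will be app acceptability and functionality, measured with" the SUS. It explains the scale as "scores range from 0-100 and total score over 70 yielding satisfactory usability and user acceptance". Several further primary measures follow. Nothing later in the document withdraws SUS or gives it a schedule of its own.
- **Procedure, timing:** "Measures will be obtained at baseline and 42 days later". SUS is not exempted.
- **Procedure, arms:** "The control group receives no further contact, access to the application or information until study-end questionnaire measures". For the other two schools, "Participants in both the TAU group and the intervention group receive an approximately 10 minutes long introduction regarding the study specifications and the application". Also, "Participation in the TAU group and intervention group is defined as downloading the Sidekick app and completing at least 3 health exercises within it".
- **Statistical analysis** lists correlation, t-tests, repeated measures ANOVA and chi-square tests for "mean differences from baseline to trial's end within and between research groups on primary and secondary outcome measures". SUS is not exempted here either, and no method is set against 70.

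**The concern.** SUS asks respondents to rate a product they have used. The general analysis sentence treats it like a symptom score that every pupil in every school can supply at both times. Followed literally, it calls for a pre-use rating in the two app schools, and for a rating in a school where there is nothing to rate.

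The question SUS can answer is how usable the pupils who tried the app found it, set beside the cut-off the document cites. That question has no planned estimate. It also has no defined population, which matters in a trial about attrition. Pupils who gave the app up because they disliked it may be the least likely to rate it. If motivational support changes attrition, which is what the trial sets out to learn, any such selection would also differ between the two app schools.

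**Working it through.** The plan gives no SUS mean, SD, target difference, sample size or retention rate, so there is no design figure to reproduce. The check is mainly one of logic.

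**Step 1. Which SUS quantities can be obtained?**

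| School | SUS at baseline | SUS at day 42 | Change score |
|---|---|---|---|
| Control | no app to rate | no app to rate | none |
| TAU | before use | obtainable | not meaningful |
| Intervention | before use | obtainable | not meaningful |

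The baseline entries for the app schools need a caveat. The roughly 10-minute introduction is not placed before or after the baseline measures, so a first impression might be recorded. But the Statistical analysis section starts the trial period at the first completed in-app exercise, and a rating taken before that is not a rating of use.

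So a meaningful change score exists in 0 of 3 schools, and no contrast with control is meaningful. Two things remain: the day-42 level in each app school, and the day-42 difference between them.

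**Step 2. Is anything planned against 70?** No. None of the listed methods refers to it. The document does not say whether it applies to a mean or to a proportion of pupils, in which school, or among whom.

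**Step 3. Could the choice of population matter?** Every mean and SD from here on is an assumption, used only to see whether the answer can change. Let *r* be the share of app users still using the app at day 42. Take the extreme case in which all of them answer and no leaver does.

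All-user mean = *r* × (mean of continuing users) + (1 − *r*) × (mean of leavers)

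With 75 for continuing users and 60 for leavers:

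- *r* = 0.2: 0.2 × 75 + 0.8 × 60 = 63.0
- *r* = 0.3: 0.3 × 75 + 0.7 × 60 = 64.5
- *r* = 0.5: 0.5 × 75 + 0.5 × 60 = 67.5
- *r* = 0.7: 0.7 × 75 + 0.3 × 60 = 70.5

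The observed figure would be 75 throughout. The all-user mean reaches 70 when *r* = (70 − 60)/(75 − 60) = 0.67.

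The gap between the groups drives this, so it must vary too. For continuing-user means of 72 to 80 and leaver means of 50 to 65, the retention needed runs from (70 − 65)/(80 − 65) = 33% to (70 − 50)/(72 − 50) = 91%.

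**Step 4. How precise would an estimate against 70 be?** The 95% half-width is 1.96 × SD/√n. For assumed SDs of 12.5 to 20, ignoring clustering, the observed mean must be at least 72.5 to 73.9 with n = 100, or 73.5 to 75.5 with n = 50, for the interval to lie above 70.

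**The case against.** The strongest reply is that the plan can still yield a SUS result, and much of that reply stands.

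- A reader might infer that no SUS analysis is possible. The documents do not support that. Both app schools use the app, independent samples t-tests are listed, and a day-42 comparison of the two is feasible.
- A reader might take 70 as a declared success criterion left untested. It is not one. The document gives it as the scale's interpretive cut-off, just as it gives a T-score cut-off for the anxiety and depression scale. No hypothesis or pass rule uses it.
- A reader might infer that SUS is limited to pupils still using the app. Nothing says so. Attrition is defined by the last completed in-app exercise, not by failing to answer a questionnaire. Study-end questionnaires go even to the control school, so they do not depend on app use.
- The background remark that attrition is generally high refers to other mobile interventions and gives no rate.
- The stated aims are attrition and health behaviour. Usability is not named among them.

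Two things are left after this. The one analysis rule that covers SUS does not work for it. And silence about the population is not protection: the participation definition could exclude pupils who gave up before three exercises, and no rule covers missing scores.

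**Conclusion.** The point holds as a mismatch between a named primary outcome and its planned analysis. The change score and every contrast with control are not meaningful for SUS. Day-42 scores in the TAU and intervention schools are meaningful, but they have no planned estimate against the only benchmark cited and no stated population.

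Selection towards pupils who liked the app is a risk, not a demonstrated bias. Its direction rests on the assumption that leavers rate the app lower and answer less often. Its size cannot be given, because the documents contain no SUS values and no retention rate. The illustration shows only that the conclusion against 70 can change within a wide range of assumptions, which is reason enough to fix the population in advance. It does not show that the users-only figure would mislead by any particular amount.

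The change should be made: SUS is listed first among the primary outcomes, and the repair is mostly wording.

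**What to change.** In Measurements, Procedure and Statistical analysis:

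1. Remove SUS from the change-from-baseline analysis and from all comparisons with the control school.
2. Collect SUS in the day-42 questionnaire from every TAU and intervention pupil who opened the app, including those who stopped and those with fewer than 3 exercises. State that this departs from the participation definition for this outcome.
3. Report the mean with a 95% CI against 70 in each app school. Show scores separately for pupils still using the app and those who had stopped, and draw the acceptability conclusion from all app users.
4. Report the SUS response rate by usage status and add a sensitivity analysis for missing scores. One simple form gives the mean that non-responders would need for the overall mean to equal 70: (70 − *q* × respondents' mean)/(1 − *q*), where *q* is the response rate. For example, with *q* = 0.5 and a respondents' mean of 75, it is (70 − 37.5)/0.5 = 65.
5. Present the TAU–intervention difference as descriptive. With one school per arm it cannot be separated from a difference between schools.

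The cost is a few sentences, plus the effort of reaching pupils who stopped. The SUS mean will probably be less favourable, and those pupils will be rating the app some time after they last used it.

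### Daily physical activity is a primary measure recorded only in the app, so the promised baseline-to-end comparison is impossible in or against the control arm and has no pre-app baseline in any arm

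*Combined protocol and SAP*

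**What the plan says.** The Measurements section lists the System Usability Scale (SUS) first among the primary outcomes and then adds: "Further primary measures were amount, frequency and time of daily physical activity measured through in-app activity". No other instrument for physical activity is named.

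The Procedure section allocates one school each to control, TAU (app without motivational support) and intervention (app with support), with measures at baseline and 42 days later. Of the control school it says: "The control group receives no further contact, access to the application or information until study-end questionnaire measures". Weekly feedback, competitions and rewards for usage go to the intervention arm only.

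The Statistical analysis section promises mean differences from baseline to the end of the trial "within and between research groups on primary and secondary outcome measures". It also fixes the clock: "Trial beginning is defined as time of first in-app health exercise completion". Attrition is timed at a participant's "last completed health exercise in SidekickHealth".

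The second aim, stated at the end of the introduction, is to examine whether the intervention increases daily mental, nutritional and physical health behaviour.

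**The concern.** A baseline-to-end comparison across three arms needs a value in each arm at each time. For this outcome the measuring instrument is part of the intervention. The arm without the app has no instrument, and the arms with it have none until they start using it. Anyone following the plan literally finds that the promised test cannot be run where the control arm is involved.

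What can be run is a comparison of what two groups logged. One of those groups is rewarded for using the app, and that means for logging. A higher figure there could be reported under the second aim as more physical activity when part or all of it is longer or fuller recording. The plan holds no direct, app-independent measure of activity against which to check such a report.

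**Working it through.** The plan gives no figure to reproduce. The question is which data can exist.

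**Step 1. Fill the arm-by-time cells.** Inputs: three arms and two times (Procedure); the app as sole instrument (Measurements); no app in control (Procedure); record starting with app use (Statistical analysis). 3 arms × 2 times = 6 cells.

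| Arm | Before app use | During the 42 days |
|---|---|---|
| Control | none, no app | none, no app |
| TAU | none, app not yet used | value, until last use |
| Intervention | none, app not yet used | value, until last use |

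Cells that can hold a value: 2 of 6.

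**Step 2. Count the comparisons.**
- Within-arm change from a pre-app baseline: 0 of 3 arms.
- Between-arm contrast of that change: 0 of 3 pairs.
- Between-arm contrast of on-study level: 1 of 3 pairs (TAU v intervention).
- Early-use v late-use change: computable in 2 of 3 arms. The early value is taken after exposure has begun, and no early or late window is defined.

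The counts are the same for amount, frequency and time, since all three come from the app.

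**Step 3. What the one remaining contrast measures.** As a simplification, let an arm's mean recorded 42-day total be r × c × T. Here r is true mean daily activity, c the share of it that is logged while the app is in use, and T the mean days in use (at most 42); r and c are taken as unrelated to T. Then

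recorded ratio (intervention / TAU) = (r_I / r_T) × (c_I / c_T) × (T_I / T_T).

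Only the first factor is behaviour. Dividing by days in use removes the third factor but leaves the second. The documents give no value for r, c or T, so neither the size of the recording part nor its share of any difference can be derived. If use lasts equally long and logging is equally complete in both arms, the recording part is 1. The word daily in the outcome does not settle the denominator: it can mean per calendar day or per day in use.

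**Step 4. Look for another measure.** The listed secondary instruments are BMI-SDS, RCADS (anxiety and depression), GSE (self-efficacy) and BEARS (sleep). None of the four measures activity or diet directly. BMI-SDS does not depend on the app but is at most an indirect marker.

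**The case against.** **The plan does not say pre-app.** It says baseline, and it dates the trial from the first in-app exercise. Early use could therefore serve as baseline in the two app arms. This stands. A reader might infer that no change of any kind can be computed in any arm, and the documents do not support that. In the app arms the defect is an on-treatment baseline and an undefined window; in the control arm the comparison is impossible.

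**TAU v intervention is a legitimate contrast.** Motivational support is the stated difference between these arms, and the independent-samples t-tests in the plan suit it. Some activity is tracked by GPS rather than typed in, according to the mHealth application section. This also stands, so it would go too far to call any difference a recording artefact. But GPS tracking still needs the app in use, so the two explanations remain mixed.

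**Outcome and usage may not be the same variables.** A reader might infer that the plan uses identical quantities as behavioural outcome and as usage, since the Cox model addresses "attrition prediction based on usage of in-app health exercises between time, type and frequency of exercises". The documents do not establish this. The Procedure definitions ("Exercise frequency refers to how often a given exercise was completed by a participant" and "Time of exercise is defined as the timestamp on completion of exercise within any of the three types of exercise categories") cover nutrition and mental health as well. Time is a timestamp there, whereas in the outcome it may mean duration. The point does not rest on this identity.

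**Other primary measures and the first aim.** It would also go too far to say that the primary outcomes fail as a group. SUS rates the app and needs no control value. Stress, sleep quality and energy are called self-reported, so a questionnaire reading is plausible. The attrition analyses need neither a control value nor a pre-app baseline. The point concerns physical activity and the second aim.

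**Control could be set to zero.** This fails. Pupils in the control school may be active but have nowhere to log it, so a zero would be imputed by design and not measured.

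**Conclusion.** The concern holds for in-app physical activity. The promised baseline-to-end test cannot be run in or against the control arm, and no arm has a pre-app baseline: 2 of 6 cells can be filled, and 1 of 3 between-arm contrasts of on-study level is available. Applied as written, the plan gives either no result or a difference in logged activity that can be mistaken for a change in behaviour.

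This rests on two readings: that the app is the only source for the outcome, as Measurements states, and that the control school has no app during the trial, as Procedure states. No size can be given for the recording effect. It may be nil or it may account for the whole of an observed difference.

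**What to change.** In the Measurements and Statistical analysis sections:

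1. Describe in-app physical activity as logged activity, an engagement outcome compared between TAU and intervention only, over a fixed 42 days. State whether it is a 42-day total or a mean per day in use.
2. Remove it from all control-arm tests and from the baseline-to-end tests. If an early v late contrast is kept, define both windows and label it on-treatment and descriptive.
3. Limit three-arm tests to measures collected in all schools at both times.
4. State that the trial has no controlled measure of physical activity. Report a TAU v intervention difference as a difference in logged activity, not as a demonstrated change in physical activity under the second aim.

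This needs new wording and no new data. The trial gives up a behaviour-change claim on this outcome that its design cannot support. Keeping a controlled claim would need an app-independent activity measure in all three schools at baseline and day 42. That is new data collection, and it is possible only if baseline has not yet been taken.
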